## 2 STATEMENT OF COMPLIANCE

This study will be conducted in accordance with the Code of Federal Regulations on the Protection of Human Subjects (45 CFR Part 46), 21 CFR Parts 50, 56, 312, and 812 as applicable, any other applicable US government research regulations, and institutional research policies and procedures. The International Conference on Harmonization ("ICH") Guideline for Good Clinical Practice ("GCP") (sometimes referred to as "ICH-GCP" or "E6") will be applied only to the extent that it is compatible with FDA and DHHS regulations. The Principal Investigator will assure that no deviation from, or changes to the protocol will take place without prior agreement from the sponsor and documented approval from the Institutional Review Board (IRB), except where necessary to eliminate an immediate hazard(s) to the trial participants. All personnel involved in the conduct of this study have completed Human Subjects Protection Training.

CONFIDENTIAL

The information contained in this document is confidential and the sole property of "Check-Cap"  
Any reproduction in part or whole without the written permission of "Check-Cap" is prohibited

	Document Title	Clinical Investigational Plan For Study CL-SY-02-0096		
	Document No.	DOC001593	Revision	03

#### 4 CLINICAL INVESTIGATION SUMMARY

Protocol Title	Evaluation of safety, usability and subject compliance while using Check- Cap's C-Scan System for providing structural information on colonic polypoid lesions and masses			
Study Number	CL-SY-02-0096			
Sponsor	Check-Cap, Inc.			
Study Design	Prospective, Multi-center, Single-arm, safety study			
Purpose	To demonstrate the safety of the Check-Cap C-Scan System			
Study Centers	Up to two (2) centers located in the United States			
Number of Participants	45 healthy subjects			
Investigational Device	Check-Cap's C-Scan System comprises C-Scan Capsule, C-Scan Track and C-Scan View.  The Check-Cap C-SCAN System is an ingestible capsule system intended to provide structural information on the endoluminal surface of the colon for the detection of colon polyps. It is intended for use in adults at average-risk for CRC who are not candidates for colonoscopy or who decline colonoscopy, or patients who had an incomplete optical colonoscopy.			
Intended use				
Primary Objective	To evaluate the safety of the Check-Cap C-Scan System.			
Secondary Objectives	
 
• To evaluate subject's compliance
 
• To evaluate subject's satisfaction
 
• To collect data to improve the product's algorithm
 
			
Primary Safety Outcome Measure	Incidence of device and procedure related Serious Adverse Events (SAE)			
Secondary Outcome Measures	
 
• Subject compliance
 
• Subject satisfaction
 
• Procedure related data for improvement of algorithm:
 
• Battery life Assessment
 
• Device performance
 
			
Inclusion Criteria	
 
1. Patients age 40 years or older
 
2. Able to provide a signed informed consent.
 
3. Willing and able to comply with the specified study requirements and follow-up evaluations, and can be contacted by telephone.
 
4. Able and agrees to undergo colonoscopy procedure.
 
5. Body Mass Index (BMI) > 19 and ≤ 35.
 
6. Maximum body (abdominal) circumference < 120 cm.
 
7. A colonoscopy procedure is pre-scheduled within 60 days
 
			
Exclusion Criteria	
 
1. Subject who is not a suitable candidate for a colonoscopy (i.e., moderate sedation)
 
2. Known history of dysphagia or other swallowing disorders.
 
3. History of the followings: Inflammatory Bowel Disease (IBD) including Crohn's disease or Ulcerative, Colitis, Meckel's Diverticulum, Bowen Hernia, known fistulas or strictures (doctors' discretion), or a history of small bowel obstruction.
 
4. Known motility disorders: 
 
a. Chronic Constipation: less than 3 bowel movements/week, w/out the use of laxatives.
 
b. Delayed gastric emptying.
 
c. Narcotic use
 
 
 
5. Prior history of abdominal surgery that might cause bowel strictures leading to capsule retention, as determined by physician discretion with the exception of appendectomy, cholecystectomy and hysterectomy
 
6. Any condition believed to have an increased risk for capsule retention, strictures,
 
			

	Document Title	Clinical Investigational Plan For Study CL-SY-02-0096		
	Document No.	DOC001593	Revision	03

	
bowel adhesion or 'obstacles' to free passage of the capsule (such as intestinal tumors, radiation enteritis) or incomplete colonoscopies(e.g. due to obstructions or non-steroidal anti-inflammatory drugs (NSAID) enteropathy) as determined by physician discretion.
 
 
7. Has a cardiac device (e.g. pacemaker or Implantable Cardioinverter Defibrillator (ICD)) or any other implanted active device
 
8. Known sensitivity to iodine, or with known kidney failure.
 
9. Known condition which precludes compliance or is contraindicated with study and/or device instructions.
 
10. Has a Magnetic Image Resonance (MRI) procedure scheduled within 1 month
 
11. Known condition of drug abuse and/or alcoholism.
 
12. Women who are either pregnant or nursing at the time of screening (to be verified by urine or serum pregnancy test for woman of child- bearing potential who are not post-menopausal or undergone surgical sterilization.
 
13. Concurrent participation in another clinical trial using any investigational drug or device.
 

Study Duration	The total study duration across all patients is expected to be approximately 6 months, dependent upon subject recruitment rate.
Participant Duration	The duration of study participation for each subject is expected to be approximately 8-10 weeks.

	Document Title	Clinical Investigational Plan For Study CL-SY-02-0096		
	Document No.	DOC001593	Revision	03

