## 10 STUDY OBJECTIVES

### 10.1 Primary Objectives

To evaluate the safety of the Check-Cap C-Scan System.

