### 10.3 Primary Safety Outcome Measure

The safety of the Check-Cap System will be evaluated by the incidence of device or procedure related Serious Adverse Events (SAE), as adjudicated by the Independent Physician Adjudicator.

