## 14 STATISTICAL ANALYSIS

### 14.1.1 Sample Size Considerations

This is a pilot safety study; therefore, sample size is not determined by power analysis. Up to 45 subjects will be recruited to the study.

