### 14.1.2 Primary Analysis Set

The primary objective of the study is to establish the safety of the Check-Cap C-Scan system. The primary analysis set for establishing the safety of the Check-Cap C-Scan system will include all subjects who underwent C-Scan procedure per protocol.

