### 14.1.4 Data analysis

Descriptive statistics for all parameters will be calculated. For continuous parameters descriptive statistics including mean, standard error, median, minimum, and maximum values will be reported overall and at each time-point. For ordinal parameters, counts and percentages may be reported in addition to the mean, standard error, median, minimum, and maximum values. Categorical parameters will have counts and percentages reported overall and at each time-point.

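### Two sections promise to demonstrate or establish safety, while the primary SAE incidence of an unpowered pilot is reported without any measure of precision

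*Combined protocol and SAP*

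**What the plan says.** The plan words one objective at two strengths.

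- **Stronger.** The Purpose row of the summary (section 4) reads "To demonstrate the safety of the Check-Cap C-Scan System". Section 14.1.2 reads "The primary objective of the study is to establish the safety of the Check-Cap C-Scan system".
- **Softer.** Section 10.1, like the Primary Objective row of the summary, reads "To evaluate the safety of the Check-Cap C-Scan System". The protocol title also speaks of evaluation.

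The primary outcome in section 10.3 is the "incidence of device or procedure related Serious Adverse Events (SAE), as adjudicated by the Independent Physician Adjudicator".

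On size, section 14.1.1 states: "This is a pilot safety study; therefore, sample size is not determined by power analysis". It adds: "Up to 45 subjects will be recruited to the study". The primary analysis set in section 14.1.2 "will include all subjects who underwent C-Scan procedure per protocol".

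On analysis, section 14.1.4 is descriptive: "Categorical parameters will have counts and percentages reported overall and at each time-point". It lists a standard error for continuous and ordinal parameters but no measure of precision for categorical ones. Section 14 contains no confidence interval, acceptable SAE rate or success criterion for the primary outcome. The only numerical acceptance criterion among the outcome measures is for satisfaction (section 10.4, average score above 3.5).

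**The concern.** To demonstrate or establish safety implies that the data can rule out an unacceptable event rate. That takes either a stated maximum rate or, at the least, an interval showing which rates remain possible. The plan offers neither for its primary outcome.

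This matters because zero is a likely result: section 8 reports no device- or procedure-related SAE among more than 220 earlier volunteers. Zero events is also where a percentage says least about precision, because 0% looks the same whether 10 or 1,000 subjects stand behind it. Set beside a purpose worded as demonstration, an unqualified 0% invites a conclusion that the sample cannot carry.

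**Working it through.** The plan states no power, significance level, margin or interval width, so it has no design figure to reproduce. The question is what the primary outcome could show with zero events.

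**Inputs**
- Maximum number of subjects: 45 (section 14.1.1), a ceiling and not a fixed number.
- Outcome: a subject has, or does not have, at least one related SAE (my per-subject reading of section 10.3).
- Confidence level: 95%, assumed, since the plan gives none.

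**Zero events, all 45 analysed.** The exact (Clopper-Pearson) upper limit for 0/n is 1 − (α/2)^(1/n) two-sided and 1 − α^(1/n) one-sided.
- Two-sided: 1 − 0.025^(1/45) = 0.0787, or 7.9%.
- One-sided: 1 − 0.05^(1/45) = 0.0644, or 6.4%.
- The Wilson two-sided limit is also 7.9%, so the result does not hinge on the choice between these two methods.

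**Chance of seeing no event when the true rate is p**, (1 − p)^45:
- p = 2%: 0.98^45 = 0.403, about 40%.
- p = 5%: 0.95^45 = 0.099, about 10%.

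**Fewer than 45 analysed.** The per-protocol restriction in section 14.1.2 can lower the denominator, as can the discards in section 14.1.3 if they apply to this set. In the previous study (section 8.1), 3 of 66 subjects failed to ingest the capsule. The same proportion here would leave 45 × 63/66 ≈ 43. The other numbers below are assumed.

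| Number analysed, 0 events | Two-sided 95% upper limit | One-sided 95% upper limit |
|---|---|---|
| 45 | 7.9% | 6.4% |
| 43 | 8.2% | 6.7% |
| 40 | 8.8% | 7.2% |
| 35 | 10.0% | 8.2% |

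**One event in 45.** The estimate is 1/45 = 2.2%. The exact two-sided 95% limits are the 2.5% quantile of Beta(1, 45) and the 97.5% quantile of Beta(2, 44), which give 0.06% to 11.8%.

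**The case against.** The strongest reply is that this study is a pilot and says so. The title, the formal objective and the outcome section all speak of evaluation; the stronger verbs appear only in the Purpose row and in section 14.1.2. This stands in large part. A small, unpowered sample is not a defect in a pilot, and the formal objective already has the right wording. What remains is that the statistics section, where the primary analysis is defined, uses the stronger word.

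A reader might infer that the plan would treat zero events as proof of safety. The documents do not support this: section 14 has no hypothesis, decision rule or success criterion. The nearest support is section 8.1, which concludes that the previous study showed the procedure to be safe because no device-related SAE occurred. That is background narrative, and it appeals to all C-Scan trials. It shows how a zero could be read, not how this plan says it will be read.

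A reader might also take 7.9% as a plausible true rate. It is only the upper limit from this study alone. For illustration, 0/220 from the earlier experience would give 1 − 0.025^(1/220) = 1.7%. Those subjects used various versions of the capsule, and this plan does not pool them, so that figure does not replace the study's own interval; it does argue against alarm.

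Finally, counts will be reported, so anyone can calculate the interval afterwards. That is true, and no data are lost. But the precision of the primary outcome should be part of the pre-specified result and not be left to the reader.

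**Conclusion.** The point holds as a mismatch between wording and analysis. *Demonstrate* (section 4) and *establish* (section 14.1.2) claim more than this pilot can show and conflict with *evaluate* in the formal objective. The primary outcome carries no measure of precision. With zero events in all 45 subjects, true rates up to 7.9% remain compatible with the data, and the limit rises as the number analysed falls.

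These figures assume a 95% level and a per-subject binary outcome. On the one-sided convention the limit for 45 subjects is 6.4%.

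The design, the sample size and the validity of the data are not in question, and the plan does not state that zero events proves safety. This is an inexpensive improvement that should be made before the data are seen.

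**What to change.** 1. **Section 14.1.4.** Define the primary result as the number of subjects with at least one device- or procedure-related SAE, adjudicated as in section 10.3, over the number analysed. Report it with an exact (Clopper-Pearson) two-sided 95% confidence interval.
2. **Sections 4 and 14.1.2.** Replace *demonstrate* and *establish* with *evaluate* or *estimate*, to agree with section 10.1.
3. **Section 14.1.1.** State the expected precision as depending on the number analysed: for example, zero events gives a two-sided 95% upper limit of 7.9% if all 45 are analysed, and a higher one if fewer are. A single fixed figure would be wrong, because 45 is a maximum and the analysis set is restricted.

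The cost is a few lines of text, with no change to procedures, sample size or data collection. The drawback is that the headline result will look slightly less favourable.

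If the sponsor prefers to keep *demonstrate*, the plan would need a justified maximum acceptable rate and a sample size to match. For scale only: with zero events, a one-sided 95% upper limit below 5% needs ln 0.05 / ln 0.95, rounded up to 59 subjects; below 2% it needs ln 0.05 / ln 0.98, rounded up to 149.

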## 5 SCHEDULE OF STUDY ASSESSMENTS

Assessments	Pre-screening	Visit 1: Baseline and C-Scan	Follow-up 1: C-Scan - During Procedure follow-up	Follow-Up 2: C-Scan Procedure End follow-up Call	Follow-up 3: Colonoscopy Post Procedure follow-up Call
Visit Window	-30-0 days	0 days	0- As required days	1-3 days post procedure	1-3 days post procedure
Questionnaire	X				
Informed Consent		X			
Inclusion/ Exclusion Criteria		X			
Demographics		X			
Medical History		X			
Concomitant Medications		X			
Pregnancy test 		X			
C-Scan procedure		X			
Connect to C-Scan		X			
C-Scan capsule		X			
Ingest contrast		X	X		
FIT test			X		
Follow up phone calls 			X		
Capsule Excretion				X	
Abdominal x-ray 				X	
Subject Satisfaction Survey				X	X
Colonoscopy Report	X 				X
Follow up visit call				X	X
Adverse Events		X	X	X	
Study Exit					X

Urine pregnancy test for women of childbearing potential

Minimum of two phone calls per day until capsule excretion

Abdominal x-ray ONLY if suspected that capsule has not been excreted (subject will come to office/unscheduled visit)

 Collection of a previous colonoscopy report, if available

	Document Title	Clinical Investigational Plan For Study CL-SY-02-0096		
	Document No.	DOC001593	Revision	03

## 6 ABBREVIATIONS

AE	Adverse Event
AR	Adverse Reaction
BMI	Body Mass Index
CFR	Code of Federal Regulations
CI	Chief Investigator
CIP	Clinical Investigation Plan
CMT	Compton backscattering
CPS	Capsule Positioning System
CRA	Clinical Research Associate
CRC	Colorectal Cancer
CRF	Case Report Form
CRO	Clinical Research Organization
CT	Computerized tomography
EC	Ethics Committee (see REC)
FDA	Food and Drug Administration
FIT	Fecal Immunochemical Test
FOBT	Fecal Occult Blood Test
GCP	Good Clinical Practice
GI	Gastrointestinal
GLP	Good Laboratory Practice
IB	Investigator Brochure
IBD	Inflammatory bowel disease
ICD	Implantable Cardioinverter Defibrillator
ICF	Informed Consent Form
ICH	International Conference of Harmonization
IFU	Instructions for Use
IRB	Institutional Review Board
Max	Maximum
Min	Minimum
MRI	Magnetic Resonance Imaging
NAMSA	North American Scientific Associates
NSAID	non-steroidal anti-inflammatory drugs
PI	Principle Investigator
RA	Radioactive
RF	Radio frequency
SAE	Serious Adverse Event
SCA	Scan Control Algorithm
StD	Standard deviation
SOP	Standard Operating Procedure
TMF	Clinical investigation Master File
TTT	Total Transit Time
UADE	Unanticipated Adverse Device Effect
XRF	X-ray Florescence

	Document Title	Clinical Investigational Plan For Study CL-SY-02-0096		
	Document No.	DOC001593	Revision	03

## 7 INTRODUCTION

### 7.1 Colorectal Cancer Screening

Colorectal cancer (CRC) is the third leading cause of cancer death according to the American Cancer Society but is largely preventable. Approximately 97,000 new cases of colon cancer will be detected in the United States annually, with over 50,000 deaths. Studies published in the early 1990s, showing that screening for CRC can reduce CRC -related mortality, led many organizations to recommend screening in asymptomatic, average-risk adults older than 50 years. Since then, however, national screening rates remain low in most countries. For example, in the United States for adults age 50 and older, colorectal cancer screening was 63% in 2015, Canada 16% (2011), Spain 49.2% (2014) and the Netherlands 68.2% (2014), including the United States and Europe. Several important studies published over the past four years have refined our understanding of existing screening tools and explored novel means of screening and prevention

In an attempt to reduce this cancer related death, legislation was passed in both the US and Germany in 2002, which establishes by law, reimbursement for screening colonoscopy in the population 50 years and older in the US, and 55 and older in Germany. This has increased the potential number of screening colonoscopies in these 2 countries alone to 15 million colonoscopies a year.

Current strategies to prevent CRC vary considerably with regard to effectiveness, up-front costs, risks, and invasiveness. New CRC screening tests such as Fecal Occult Blood Test (FOBT) and Fecal Immunochemical Test (FIT) detect blood in the stool, where fresh or occult is a sensitive indicator for the presence of an advanced adenoma or cancerous tumor which are typically bleeding due by angiogenesis – a proliferation of blood vessels in the polyp. FOBT and FIT do not provide structural information of the colon and by that fail to diagnose non-cancerous as well as adenomatous polyps. They are one mechanism to improve adherence. Screening of the colon can be performed by Sigmoidoscopy, endoscopic colonoscopy and virtual colonoscopy. Sigmoidoscopy, endoscopic colonoscopy and virtual colonoscopy are invasive and require cleansing of the colon. Patients are required to conduct a rigorous preparation for cleansing of the colon. Stool DNA (ColoGuard) is another recently added test for detecting CRC by identifying specific DNA markers which were carried by the Stool from a cancerous tumor in the colon.

The colon preparation process is regarded as one of the main objections of patients, and many choose to forgo completion of a scoping procedure as a result. Additionally, for patients with advanced cardiac disease, undergoing antithrombotic therapy, considered at high risk to undergo sedation or who have kidney diseases which might be compromised by cleansing preparations, scope procedures may pose a problem to the patient. Therefore, a technology whereby structural information could be provided, yet does not require rigorous cleansing of the colon and is not considered invasive would be beneficial to patients.

### 7.2 C-Scan Technology

The technology of the Check-Cap Imaging System is based on a low dose radioactive (RA) sealed source embedded in the C-Scan capsule which radiates X-Rays through a collimator to all directions. The capsule is designed to start scanning once it reaches the cecum and the X-ray is emitted when the capsule is propagating along the colon during contraction of the walls. While stationary (which is most of the time) the capsule is set at an idle mode and the radiation X-ray source is blocked by the collimator. The transit time of the capsule in the colon might vary from 24-100 hours, pending the typical bowel activity of the subject. The capsule is powered by onboard batteries and is designed to operate up to 100 hours.

	Document Title	Clinical Investigational Plan For Study CL-SY-02-0096		
	Document No.	DOC001593	Revision	03

The C-Scan is designed to be ingested without any cleansing of the colon and travel through the gastrointestinal (GI) tract naturally while the subject continues daily activities, including eating normally. During C-Scan procedure the subject swallows a capsule and capsule travels painlessly through the gastrointestinal tract, identifying polyps, the precursors of colorectal cancer. In order to increase the contrast of the colon's walls and to differentiate them from their content, it is essential to increase the stool's contrast by ingesting radio-opaque material. It is a standard procedure using approved Iodine based liquids, contrast agents such as (Telebrix or Omnipaque) at the discretion of the hospital similar to the preparation to abdominal computerized tomography (CT).

During the passage of the capsule in the gastrointestinal tract, it transmits information to a recorder attached to the back. In order to collect data about the instantaneous localization of the capsule traveling in the colon additional sensors are embedded in the recorder on the back side. A commercial wrist watch is supplied (optional) with the C-Scan system for use by the subject during the procedure. The watch is tuned to 'listen' and display the information transmitted from the capsule to the Track. The watch is a monitoring tool to optimize data interpretation during the clinical study and is not an integral part of the C-Scan system.

After the capsule is expelled, the data from the recorder is downloaded to an acquisition workstation. Later, the data is transferred to a processing workstation and analyzed to create a map of the colon. The current C-Scan system is designed to operate for up to 100 hours. The average radiation dose calculated from these procedures is 52 uSV (typical results from last study: StD 38, Min. 19, Max. 165 uSV) – this is equivalent to one chest X-ray radiation.

	Document Title	Clinical Investigational Plan For Study CL-SY-02-0096		
	Document No.	DOC001593	Revision	03

## 8 PREVIOUS STUDIES

More than 220 volunteers have ingested the C-Scan capsule in its various versions. Three subjects failed to ingest the capsule due to Acataposis. All capsules except four were captured and returned by the subjects. All returned capsules were tested in Check-Cap laboratories and their sealing and structure were verified.

The average transit time estimated from the last 63 procedures (CE study) was ~52 hours with 32h StD. In most cases the capsule arrived to the caecum within 24 hours (average 16 hrs.) and the motility through the colon was 16 hours (with 32h StD).

Some subjects reported mild diarrhea or mild discomfort, all events resolved within few hours w/out any intervention. No capsule retention (more than 300 hours per protocol) had been reported to date. In one case the capsule was retrieved by colonoscopy after 100+ hours in the caecum. The 'post' colonoscopy was rescheduled earlier according to the request of the participant. Three serious adverse events were reported, although, none were device or procedure related. All events were resolved without the need of medical intervention.

